5.4 Data Analysis

To include:

- *Specifically what data sets will be collected (name, date of birth, email address, ethnicity, health status, financial records, IP address etc.)*
- *whether this data will be collected directly from participants (e.g. via questionnaires/interviews) or indirectly, from a third party (previously collected data set) and how i.e. web form, online application, paper form*
- *Detail the analysis methods that will be undertaken e.g. content analysis, framework analysis, interpretative phenomenological analysis etc. and any statistical analyses.*
- *Describe how and by whom any data will be transcribed, coded, de-identified, stored, transferred, accessed, archived*
- *Any software used in the analysis should be specified and detailed how it will be used in the project*

The data will be collected directly from participant responses to the anonymous survey described above. No IP addresses will be collected. The data will be downloaded from Qualtrics into an SPSS file that is then stored in password protected files on the University of Warwick's servers.

The data will be analysed by [name] using SPSS. All of this software is provided by the University of Warwick.

As a reminder this is a pilot study and our analyses are designed to inform a future study, for which we will seek future ethical approval early in 2021.

The primary analysis will only include those participants who have not yet vaccinated. The primary analysis will be a multiple regression. Participants average political ideology scores to the conservatism scale will be mean-centred. Then Political ideology (continuous variable), Appeal type (nominal variable) and the interaction between Political ideology and Appeal type will be used to predict vaccination intentions (continuous variable). We anticipate finding an interaction effect ($\alpha < .05$).

Two check analyses will be performed. The first check is a face-validity check of the conservatism scale; this analysis will look at the correlation between participants' average political ideology scores to the 10-items and their self-reported political ideology. We expect to find a significantly positive correlation. The second check of the appeals; this analysis will look at how participants responded to the manipulation check items. We expect to find that participants who viewed the conservative appeal to have higher responses to an average of the two conservative checks than participants who viewed the liberal appeal, and vice versa.

The exploratory analysis will describe the proportion of participants that have already vaccinated, and the political ideologies, age, gender, ethnicity and current resident region of England for all participants.

For the participants who have already vaccinated, we will chart how many vaccinated on each week, up to the week the survey is disseminated. We will also describe the proportion who take up the vaccination at different locations, and the proportion who did so with a friend or family member. The reasons participants give for vaccinating will be thematically analysed. Lastly, we will describe the proportion of these participants who express some intention to engage in the spill-over behaviours: taking up the COVID-19 vaccination when it becomes available and wearing a face-mask in a store that does not require it.

For the participants who have not already vaccinated, we will assess whether the participants' demographic characteristics are similar across the randomly allocated groups using t-tests (for age) and chi-square tests (for categorical variables). Then, for each group we will describe the proportion who express some intention to be vaccinated, not to be vaccinated, and who neither agree nor disagree with the intention item. The reasons participants give for their responses will be thematically analysed. Lastly, we will describe the proportion of participants who express some intention to engage in the spill-over behaviours: taking up the COVID-19 vaccination when one becomes available and wearing a face-mask in a store that does not require it.

SECTION 6: RECRUITMENT

6.1 State the total number of planned participants and the sampling strategy; provide justification for this:

To include:

- *The rationale behind the proposed size of the sample*
- *Will the sample size provide enough data to answer the research question?*
- *If sampling will be continued until saturation is reached, then this should be stated and linked to the research question*
- *Sampling strategy- is this random, snowball, purposive, convenience etc.*
- *What is the rationale for this- it should reflect the methodological framework for the study*

The proposed sample size is 200.

Rationale/Sufficient size: This is a pilot study. The sample size is informed by a previous study (Kidwell et al 2014, Study 1) where 82 participants took part. We are recruiting more participants for two reasons. First, we anticipate some (maybe up to 50%) of our participants will have already taken up the vaccine by the time this survey is approved to conduct. Therefore the number of participants available for our primary analysis described in section 5 may only be 100. Second, 100 is still more than Kidwell's study 1, and this may allow us to detect smaller differences between groups. If the results of this pilot study support a full study, we will seek ethical approval for that full study and include in our application a sample size calculation informed by the effect size found in this study.

Rationale/Strategy: The sampling strategy is a sample of convenience of Prolific Academic UK panellists. Recruitment will be stratified using the Prolific's "Political Party Affiliation UK" pre-screening question, such that 100 opportunities to take part will be made available to panellists who identify with the Labour party and the remaining 100 opportunities to panellists who identify with the Conservative party.

To be clear, participants will not be asked what party they affiliate with in our survey, rather participants have already indicated which party they affiliate with in their Prolific Academic profile.

Prolific panellists have consented to their pre-screening responses being used in this manner. This recruitment stratification will maximize the opportunity to have a balanced set of responses across political orientations for our primary analysis described in section 5. It is important to ensure that participants represent two major political parties, because we hypothesize that differences in political orientation will affect responses to health promotion appeals. We recognize that participants' political orientation can change over time, and appreciate that the participants who choose to take part may not amount to a perfect 50:50 split. Nevertheless, we will have a balance of participants who, at one time, identified with either the Conservative or Labour party.

6.2 Where applicable, state the breakdown of participants by type and number of each type of participant, e.g. children (include age), parents, teachers, health care professionals etc.:

Type of Participant:	Number:
Identify as being affiliated with the Labour Party	100
Identify as being affiliated with the Conservative Party	100

6.3 Please provide clear inclusion criteria:

- Residence in England
- Age 50+ years old, inclusive

The age criteria is set at 50+ years old, because this is the age group currently being advised by Public Health England to seek the flu jab as soon as possible this season. (<https://www.gov.uk/government/news/most-comprehensive-flu-programme-in-uk-history-will-be-rolled-out-this-winter>).

6.4 Please provide clear exclusion criteria:

- Not a resident in England
- Age younger than 50 years old, exclusive

6.5 Please detail how participants will be recruited to the study:

To include:

- How participants will be identified/screened and approached; by whom?
- Where participants will be recruited from and when?
- Detail the source of any personal information that may be used to identify participants. If this information will be accessed by someone outside the team who would have access to this information as part of their day to day role, the reason for this should be explained, and permissions detailed e.g. healthcare, student records etc.
- Will any vulnerable groups be recruited?
- What materials will be used to recruit participants- please provide copies of posters, leaflets, invitation emails, etc.
- Where will the above materials be advertised: list and provide details of locations, websites, social media etc.
- Will any recruitment tools be used e.g. SONA- please specify and provide details.

How/Where/Source: The opportunity to participate in our study will be posted on Prolific Academic UK, an online survey platform commonly used to recruit participants to anonymous online surveys in the UK and that has been used by researchers at the University of Warwick already. For further information see: <https://www.prolific.co/>). The demographic characteristics will be set on Prolific such that the study is only available to people who have already confirmed they meet the age and resident criteria for participation.

Vulnerable Groups: No vulnerable groups will be recruited.

Advertising materials: The study description made available to participants on Prolific will read "This is a research study. If you choose to take part, you will be presented with information about influenza and asked to make choices. It may take you 8 minutes to complete. You will be compensated for your time with 1.00 GBP."

SECTION 7: INFORMED CONSENT

7.1 Please detail the process for obtaining informed consent.

Informed consent **must** be obtained prior to the participant undergoing any research activities that are specifically for the purposes of the study. This should involve discussion with potential participants or their legally acceptable representative; the presentation of written materials e.g. participant information leaflet(s) –PIL(s) and consent form, and the opportunity to ask questions.

To include:

- How and when informed consent will be obtained- written, verbal etc. provide details and justification. Justification must also be provided if informed consent will **not** be sought or if consent will be assumed (please note this needs to be appropriate to the study type).
- Who will be taking consent? What training has been undertaken for this?
- When and how potential participants will be issued with the information leaflet, in what format and how long they will be given to consider taking part?
- Does the study involve children- if so, will consent be obtained from parents, if not provide clear justification why not.
- Are the informed consent materials appropriate for the target audience- consider age / language / literacy levels / cultures etc.

As a reminder, this is an anonymous online study and an appropriate combined information / consent form has been created to contain all the recommended information. A copy of this information / consent form is available in Supporting Documents.

7.2 Please detail how participants withdraw from the study if they have requested to do so.

The process by which an individual can withdraw their participation from the study without giving a reason or experiencing any detrimental effects e.g. should they not wish to continue with their participation in an interview or focus group.

To include:

- Consideration for any data already collected up until this point- whether it is possible for this to be removed. E.g. it may not be possible to identify data once submitted for an anonymous survey. This needs to be clear in the participant information leaflet (PIL).
- Researchers should specify up to what point participants can withdraw their data from a study and **how** a participant would request this- this also needs to be clear in the participant information leaflet (PIL).
- Consideration should be given to when data will be anonymised, analysed, published etc. make sure it is possible/feasible for data to be withdrawn if this is being offered to participants. It may be appropriate to provide a time frame for withdrawal.

While taking the survey, participants can withdraw by closing their browser window. Participants will not be able to withdraw from the study after they have submitted their data. If we enabled participants to email us to withdraw their data after the survey, even with a randomly generated code, then we would be collecting identifiable data: their email addresses. As the information gathered in this survey is not sensitive, this withdraw restriction should be acceptable. Further, participants will be made aware of this withdraw restriction in the information sheet.

SECTION 8: DATA COLLECTION, USE & STORAGE (DPA 2018 & GDPR)

For projects involving processing of personally identifiable data, please answer the questions below to map the data flow to indicate the data controllers and data processors. This can be submitted as a separate document if necessary, please see accompanying guidance note from the Information Data Compliance team.

8.1 Does the project involve the collection, analysis or storage of personally identifiable data?

Yes No

'Personal data' is any information relating to an identified or identifiable natural person- a 'data subject'.

An identifiable natural person is one who can be identified, directly or indirectly, in particular by reference to an identifier (such as a name, an identification number, location data, financial data, opinion, an online identifier), or to one or more factors specific to the physical, physiological, genetic, mental, socio-economic, cultural, race, religion, trade union membership, political beliefs, medical, gender or social identity of that natural person.

If yes, please provide details of what will be collected: As described in section 8.10, the free-text spaces in our survey may allow participants to reveal unrequested identifiable information. If this happens, that information will be redacted from our data-files, as described in section 8.10.

8.2. Does the project involve the collection, analysis or storage of any personally identifiable, special category data or criminal offence data? Yes No

Special category data includes personal data which is by its nature, particularly sensitive in relation to fundamental rights and freedoms of individuals such as: racial or ethnic origin, political opinions, religious or philosophical beliefs, trade union membership, genetic data, biometric data (for the purpose of identifying a natural person), data concerning health or data concerning a natural person's sex life or sexual orientation. This type of data merits specific protection as the context of its processing. Failure to handle this data correctly could result in significant risks to the fundamental rights and freedoms of the individuals.

If yes, please provide details of what will be collected and for what purpose:

What measures are being implemented to reduce or eliminate the risk to these participants' data for the duration of the period that their personal data is collected and stored? Please see accompanying guidance note for more information.

8.3 Does the project involve the collection or analysis of personal data relating to children under 13 or vulnerable groups? Yes No

UK law provides that for data protection purposes an individual aged under 13 years old is considered a child. For the purposes of the GDPR, a child is someone aged under 16 years old, although Member States are able to reduce this age. Please consider Member State law as Parental/Guardian consent will be required for a child participating in the research.

If yes, please provide details of what will be collected:

For what purpose do you need to process the children's or vulnerable person's data?

What measures are being implemented to reduce or eliminate the risk to these participants' data for the duration of the period that their personal data is collected and stored?

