****Receiving informed consent:** Participants will read an information sheet and give their informed consent to take part in the study. The information sheet will include statements that "The views expressed in the survey are not the views of the researchers or the University, but are here to allow participants to express their own views. You may not agree with some of the statements and are free to express disagreements." Only participants who indicate meeting all the eligibility criteria and who consent to the survey will be allowed to advance.

****Demographics:** Participants will be asked their age in years (options: 50 to 99+ and prefer not to say), resident region of England (9 ONS regions: <https://www.ons.gov.uk/geography/regions>), gender identity (male, female, non-binary, other, and prefer not to say) and ethnicity (5 UK groups, and prefer not to say: <https://www.ethnicity-facts-figures.service.gov.uk/style-guide/ethnic-groups>).

****Political ideology:** Before completing a 10-item conservatism scale used in a similar study investigating the effect of messages on behaviour (Day et al 2014), participants will be reminded that "We are interested in your opinions on a variety of issues. The views expressed here are not the views of the researchers or the University, but are here to allow participants to express their own views. You are free to express agreements and disagreements. We appreciate your honest responses." The questionnaire includes two questions related to each of the five issues: one worded in conservative terms (e.g. The economic market will naturally correct itself), while the other liberal terms (e.g. The government must regulate the economy). Participants will be asked how much they disagree or agree with each statement on a seven point scale from 'strongly disagree' to 'strongly agree'. Then they will be asked to self-report their political orientation measured using a seven point scale, from very liberal to very conservative; this question will act as a face-validity check that should highly correlate with the conservatism scale.

****Vaccination against influenza in 20/21 season:** Next participants will be asked whether they received an influenza vaccination in the 20/21 season already (Yes or No).

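### Does averaging ten items, half worded conservative and half liberal, cancel out the ideology score in the primary analysis?

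*Protocol*

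**What the plan says.** Section 5.3 of the protocol takes a ten-item conservatism scale from a cited study of messages and attitudes. It covers five issues with two statements each: "one worded in conservative terms (e.g. The economic market will naturally correct itself), while the other liberal terms". Respondents are asked "how much they disagree or agree with each statement on a seven point scale from 'strongly disagree' to 'strongly agree", so agreement points in opposite political directions within each pair. A separate seven-point self-rating, from very liberal to very conservative, serves as a face-validity check and "should highly correlate with the conservatism scale".

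In section 5.4 the scale becomes the continuous predictor in the primary regression: "Participants average political ideology scores to the conservatism scale will be mean-centred". It enters together with appeal type and their interaction. The first check analysis correlates "participants' average political ideology scores to the 10-items and their self-reported political ideology" and adds: "We expect to find a significantly positive correlation".

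The protocol does not state that the liberal-worded items are reversed. It also does not state that they are left as answered.

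**The concern.** Read literally, section 5.4 averages ten answers, five of which run against the other five. Such an average reflects how readily a person agrees with statements, not where that person stands politically. The score is the moderator in the only primary test, so a cancelled score would leave the interaction almost untestable, and a null result could be taken as evidence against the alignment hypothesis. Sections 3 and 6.1 say that the effect size found here will inform the sample size of a full study, so the error would carry forward.

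The safeguard also looks loose. Section 5.3 expects a high correlation with the self-rating, while section 5.4 mentions only a significant positive one. With 200 respondents a very small correlation is significant, so a poor score might seem to pass.

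**Working it through.** **Inputs from the protocol.** Five conservative-worded and five liberal-worded items scored 1 to 7 (section 5.3); the average over ten items, mean-centred (section 5.4); 200 participants in total and perhaps only 100 in the primary analysis (section 6.1). The protocol gives no power, effect size or minimum correlation, so there is no stated figure to reproduce.

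**Step 1: the score with and without reversal.** Let c be the answer to each conservative item and l the answer to each liberal item.

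- Unreversed mean = (5c + 5l)/10
- Reversed mean = (5c + 5(8 − l))/10

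| Respondent | c, l | Unreversed | Reversed |
|---|---|---|---|
| Consistent conservative | 7, 1 | 4.0 | 7.0 |
| Consistent liberal | 1, 7 | 4.0 | 1.0 |
| Moderate | 4, 4 | 4.0 | 4.0 |
| Fairly conservative | 6, 2 | 4.0 | 6.0 |

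The arithmetic behind the concern is right. Mean-centring subtracts a constant and does not repair an unreversed score.

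**Step 2: which score the protocol describes.** Write ideology as θ (higher = more conservative), with c = 4 + aθ and l = 4 − bθ. Then:

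- Unreversed mean = 4 + (a − b)θ/2
- Reversed mean = 4 + (a + b)θ/2

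The unreversed mean rises with conservatism only if a exceeds b, and then only by the difference. The reversed mean always rises with conservatism. Against this, the protocol:

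- calls the instrument a conservatism scale, a name that fits only a score that is high for conservatives;
- takes it from a published source, where item direction is part of the instrument;
- says which statement in each pair is conservative and which liberal, which is the information needed for reversal;
- refers to "average political ideology scores to the 10-items", that is, to scores on a scale;
- expects a positive and high correlation with a self-rating that ends at very conservative.

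The unreversed mean has no reason to meet the last expectation. The reversed mean meets it by construction.

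**Step 3: what counts as significant in the check.** The smallest significant correlation is r = t/√(n − 2 + t²), two-sided at 0.05.

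- n = 200: t = 1.972, r = 1.972/√(198 + 3.889) = 0.139, r² = 1.9%
- n = 100: t = 1.984, r = 1.984/√(98 + 3.938) = 0.197, r² = 3.9%

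A small correlation would indeed be significant.

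**Step 4: would the check accept a cancelled score?** A simulation used 4,000 runs of 200 respondents, half left-leaning and half right-leaning, with seven-point items. The interaction was tested in a random 100, with an effect set to give about 75% power for the reversed score. Loadings, effect and agreement tendency are assumptions. Paired values are without / with an agreement tendency (SD 0.3).

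| Loadings, conservative vs liberal | r with self-rating, unreversed | Check passed, unreversed | Power, unreversed | Power, reversed |
|---|---|---|---|---|
| 0.60 vs 0.60 | 0.00 / 0.00 | 2.5% / 1.9% | 0.046 / 0.054 | 0.756 / 0.762 |
| 0.65 vs 0.55 | 0.154 / 0.102 | 59.0% / 28.9% | 0.090 / 0.067 | 0.752 / 0.746 |
| 0.70 vs 0.50 | 0.294 / 0.200 | 99.3% / 81.9% | 0.179 / 0.106 | 0.758 / 0.755 |
| 0.70 vs 0.40 | 0.394 / 0.283 | 100% / 98.8% | 0.295 / 0.165 | 0.739 / 0.745 |
| 0.50 vs 0.70 | −0.294 / −0.200 | 0% / 0% | 0.164 / 0.117 | 0.754 / 0.754 |

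The reversed score correlates 0.71 to 0.73 with the self-rating and passes in every run. A fully cancelled score fails in 97.5% to 98.1% of runs. An unreversed score passes often only if the conservative items load more strongly, and nothing in the protocol points to that imbalance. Even then its correlation stays below 0.40, visibly short of the high value that section 5.3 expects.

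**The case for a change.** The strongest case is that the protocol does not leave scoring entirely open. It names the operation, average and then centre, but omits the step that makes the average meaningful, and the predictor concerned carries the primary test. Stating the step would cost one sentence. It is also true that section 5.3 speaks of a high correlation and section 5.4 only of a significant one, and that a modest imbalance between the item halves would let a weak unreversed score reach significance.

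Of this, the arithmetic stands, and so does the absence of a sentence on reversal. The inference does not. Keying oppositely worded items is a standard part of scoring such a scale. It may be set out in the cited source, the survey attached to the application, or an analysis plan, none of which is at hand. Silence on it is not a statement that the items stay unreversed.

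The two remarks on the correlation do not conflict: at n = 200 a high positive correlation is also significantly positive. The sentence in section 5.4 is an expectation. No decision hangs on it, so it is not a pass mark set too low. A required minimum such as r of at least 0.5 would be a preference, not the correction of an error.

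The feared outcome would also need several signals to be missed. Section 5.4 plans to describe political ideology for all participants, and section 6.1 offers 100 places each to Labour and Conservative identifiers. A cancelled score would cluster around 4 in both groups and show almost no correlation with the self-rating. Reversal can be applied to the stored item answers at any time without loss of data.

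**Conclusion.** The concern does not hold. The fall in power from about 0.76 to about 0.05 describes an analysis that the protocol does not prescribe: it requires that oppositely worded items of a conservatism scale be averaged without keying, against the scale's name, its source and the correlation the protocol expects. Read consistently, the score separates a consistent conservative (7.0) from a consistent liberal (1.0), and the primary interaction test is unaffected.

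The fear that the check would accept a useless score fails on its own terms: full cancellation is rejected in about 98% of simulated samples, and frequent acceptance needs an assumed imbalance towards the conservative items. The step 1 arithmetic and the critical correlations depend on no assumption; the pass rates and power figures depend on the assumed loadings, agreement tendency and effect. The conclusion rests on the scale being scored in the direction its name states, which every relevant statement in sections 5.3 and 5.4 supports and none contradicts.

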As part of the fight against COVID-19, the UK government has announced its most comprehensive flu campaign to date (<https://www.gov.uk/government/news/most-comprehensive-flu-programme-in-uk-history-will-be-rolled-out-this-winter>). This should not be surprising, as every year NHS hospitals experience an overwhelming number of influenza cases, and COVID-19 increases this concern. As in previous years, the flu vaccine is free at the point of care for people 65 and over. New this year is that later in the season the vaccine will be made available free at the point of care for people 50 and over. However, if people refuse to take the vaccine this comprehensive program cannot benefit public health.

While access to vaccines remains a barrier to eradicating vaccine preventable disease in lower income countries, in higher income countries like the UK vaccine hesitancy stands in the way. In 2019, the World Health Organisation (WHO) listed increasing vaccine hesitancy as one of the ten biggest threats to global health. Recent outbreaks of vaccine preventable diseases, like measles and pertussis, are alarming. (Hotez, 2019). Over half of UK residents express vaccine hesitant attitudes (Luyten J, 2019), and a substantial proportion, 16%, already say they would refuse a COVID-19 vaccine. (<https://www.theguardian.com/media/2020/jul/07/almost-one-in-six-britons-say-would-refuse-covid-19-vaccine>; also see this report where only 53% of people are certain or very certain they would take up a COVID-19 vaccination when one becomes available: <https://www.kcl.ac.uk/news/whos-most-likely-to-refuse-a-covid-19-vaccine>).

The degree to which hesitancy is expressed varies across characteristics of the vaccine considered and the time and place it is offered, and across characteristics of the person including their perceptions of complacency, convenience, confidence, calculations, and communal responsibility, i.e. the “5Cs” (Betsch et al 2018). Information campaigns can be used to influence all the 5Cs, and public facing information is often a necessary component of public health campaigns that may also include structural components, i.e. complex interventions (Craig et al 2008). Largely, information campaigns can be viewed as a type of educational intervention.

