--Participants who say "yes", will then be asked approximately when they received the vaccination (DD/MM/YYYY), where they received the vaccination (GP, pharmacy, other) and if they went with anyone to get their vaccination (no, a friend, a family member, or someone else). Lastly, they will be asked to describe why they took up the vaccination this year in a free-text box.

--Participants who say "no", will then be randomly allocated to view one of two appeals to take up the influenza vaccination. As in Kidwell et al.'s (2013) study, one appeal aligns with a conservative ideology and the other aligns with a liberal ideology. After reading these appeals, participants will be asked about their agreement with several statements on a seven point scale; these statements are manipulation checks to verify that the appeals evoke the immediately intended foundations. Then participants will be asked whether they intend to take up the influenza vaccination this seasons on a seven point scale, from 'strongly disagree' to 'strongly agree', and then be asked to explain their answer in a free-text box.

**Spill-over behaviours: Next all participants (those who vaccinated already and those who did not) will be asked about their intentions to take up a future COVID-19 vaccination when one becomes available, and their intentions to wear a face mask in a store that does not require face masks using the same seven point scale, from 'strongly disagree' to 'strongly agree'.

**Closing: Participants who have not already vaccinated will see debriefing information that reminds them that the study should not be construed as medical advice, and that they should speak to a medical professional if they are uncertain if they should take up the influenza vaccine. Hyperlinks are provided for participants to learn more about the study this study is based on and to learn more about the UK's influenza vaccinations policies this year. We also provide them with the opportunity to tell us anything else they think is relevant to the survey in a free-text box, or write "I prefer not to say". We have found this free-text box to be useful in previous surveys to source alternative explanations for our findings.

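### Should the primary regression have included age, which is recorded before the appeals are allocated?

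*Protocol*

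**What the plan says.** Section 5.4 specifies a multiple regression with three terms: "Political ideology (continuous variable), Appeal type (nominal variable) and the interaction between Political ideology and Appeal type will be used to predict vaccination intentions". Ideology is mean-centred, and the interaction is the result the investigators anticipate. The analysis set is restricted: "The primary analysis will only include those participants who have not yet vaccinated".

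Age comes from the demographics block in section 5.3: "Participants will be asked their age in years (options: 50 to 99+ and prefer not to say"). Later in the survey, those who report no vaccination this season "will then be randomly allocated to view one of two appeals to take up the influenza vaccination". The outcome follows: "participants will be asked whether they intend to take up the influenza vaccination this seasons on a seven point scale". Age is therefore a genuine pre-allocation value.

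Among the unvaccinated, section 5.4 uses age only for description and to assess whether characteristics are "similar across the randomly allocated groups using t-tests (for age"). Section 6.1 plans 200 participants, of whom perhaps half will already be vaccinated. It intends the effect size found here to inform the sample size of a full study.

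**The concern.** A baseline variable that predicts the outcome, placed in the model as a main effect, absorbs residual variance and narrows the estimate of interest. The Protocol appears to supply a reason why age might be such a variable. Section 3 says of the established programme: "As in previous years, the flu vaccine is free at the point of care for people 65 and over". It adds that "later in the season the vaccine will be made available free at the point of care for people 50 and over". With everyone aged 50 or more eligible, the sample can straddle that boundary.

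If age did predict intention, the plan would be discarding precision from a variable it already holds, in a pilot whose interaction estimate feeds the next design. A between-arm t-test on age, with no stated consequence, might also tempt someone to adjust only after seeing the result.

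**Working it through.** **Analysis size.** 200 × (1 − 0.50) = 100, as section 6.1 states. The Protocol gives no standard deviation, effect size, power or age–intention correlation, so everything below that depends on age's predictive strength is an assumption shown over a range.

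**Validity without age.** Appeal is randomised after age is recorded, so age is independent of appeal. An omitted age main effect passes into the residual and, where age correlates with ideology, into the ideology slope. On average it does so equally in both arms, so the difference between the arms' slopes, which is the interaction, is not shifted. Two simulations with n = 100, a 7-point outcome and no true interaction agree:

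- Age in years explaining 1% to 20% of variance, age–ideology correlation 0 or 0.3, 6,000 runs per setting: rejection 3.8% to 5.0% without age and 3.9% to 5.1% with it.
- Age as 65 and over / 50 to 64 / declined, 12 settings, 4,000 runs each: 4.2% to 5.7% without age and 4.6% to 5.5% with it. Mean interaction estimates lay between −0.007 and 0.012 in both models.

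**Precision gained.** The planned model has 4 coefficients, leaving 96 residual degrees of freedom. Let R² be the share of remaining variance explained by the age term and k its degrees of freedom. Then

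SE ratio = √[(1 − R²) × 96 / (96 − k)].

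| R² (assumed) | k = 1 | k = 2 |
|---|---|---|
| 0 | 1.005 | 1.011 |
| 5% | 0.980 | 0.985 |
| 10% | 0.954 | 0.959 |

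Break-even R² is 1 − 95/96 = 1.0% for k = 1 and 1 − 94/96 = 2.1% for k = 2. For k = 2, dividing 100 by the squared ratio gives the worth of about 98, 103 and 109 participants.

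**What the age coding does.** Some participants may decline to give their age. Dropping them costs sample: with 5% missing, age must explain roughly 5% just to break even. Keeping them in a third category, with a cut at 65 to match section 3, uses k = 2. The k = 2 column then applies to variance explained by the *coded* term. If intention instead changes linearly with age, and age is taken as normally distributed, a cut that places a share p above it recovers the fraction f = φ(z)² / [p(1 − p)] of age's R², where φ(z) is the normal density at the cut.

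| Share 65+ (assumed) | f | Break-even R² for age (0.0208 / f) | SE ratio at age R² = 5%: √[(1 − 0.05f) × 96/94] |
|---|---|---|---|
| 10% | 0.34 | 6.1% | 1.002 |
| 20% | 0.49 | about 4.2% | 0.998 |
| 40% | 0.62 | about 3.3% | 0.995 |

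So when age itself explains 5% of the variance, the coding that keeps everyone yields between a 0.2% loss and a 0.5% gain in standard error.

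**Whether age is a known predictor here.** Section 3 concerns who gets free vaccine and when, not who intends to be vaccinated. Earlier free access bears first on who is already vaccinated, and those people leave the primary set. The intention item covers the rest of the season. Section 6.3 treats everyone aged 50 or more as one group being advised to seek the vaccine promptly. Nothing in the Protocol gives the strength or direction of an age effect in the set analysed.

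**The case for a change.** The best case for age is that it costs almost nothing. It is already collected, precision is scarce at 100 participants, and the worst expected penalty is about 1.1% in standard error (k = 2, R² = 0). If age explained 10% of the variance and entered as one term, an assumed 80% power would become about 84%. Writing it in beforehand would also settle what happens if the t-test on age shows a difference.

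Much of this stands as general advice. Prespecified adjustment for a strong predictor is sound practice, and the arithmetic is right on its assumptions. What does not follow is that the plan is wrong without it:

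- The benefit rests wholly on an R² that the Protocol does not supply.
- The t-test is listed among descriptive comparisons, and a chance imbalance does not invalidate the fixed model or call for a change to it.
- An age main effect would not separate an ideology-by-appeal interaction from an age-by-appeal one.
- Age in years or in bands, and what to do with those who decline, are choices on which statisticians would reasonably differ. A statistical analysis plan, not available here, is a usual place for them.

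**Conclusion.** The concern does not hold. The three-term model addresses the main objective in section 5.2, and its interaction test is unbiased with respect to an omitted age main effect and shows no material inflation of its error rate. Nothing in the Protocol is misstated or contradictory on this point.

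The possible effect on the interaction's standard error at n = 100 runs from about a 1% increase to about a 5% decrease, for an assumed R² of 0 to 10%. It is close to nil for banded age with a linear effect at 5%. This rests on 100 participants in the primary set, on R² values taken as a range because none is given, and, for the banded coding, on normally distributed age with 10% to 40% aged 65 or over. Adjusting for age would be defensible, and so is the planned analysis.
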